- **Site Meeting:** Following the online training, all site personnel will meet with study staff either in-person or via a virtual Zoom meeting. The meetings (both virtual and in-person) will be audio and video recorded using a laptop or handheld recording device (in-person meetings) or via the Zoom recording option (virtual meetings) (see “Audio/Video Recording” and “Privacy and Confidentiality” sections for more detail). These archived video files will allow for the review of meeting content by site personnel who were unable to attend the meeting live, or by those who simply wish to review the meeting discussion for a second time.

During the site meeting, study staff will briefly review online training content, allow time for the sharing of comments/questions from site personnel, and lead a discussion regarding the application of training content ideas specifically to that practice site. During this meeting, study staff will also present site personnel with their current immunization rates.

Each designated vaccine champion will track meeting attendance, and a list of practice personnel who have attended the site meeting will be e-mailed to the study coordinators and stored in a password-protected Excel/Word file. The names will not be linked with any other study data. This list will be accessed for the purposes of confirming those who should receive MOC credit.

Note: For intervention sites that have completed their site meeting during the first half of the calendar year (i.e., prior to July), site personnel may be asked to participate in a second abbreviated “flu booster” site meeting just prior to flu season of that same year (e.g., in Aug/Sept). This abbreviated meeting (approx. 15 minutes) will discuss content (see table 3) only applicable to influenza.

- **MOC/CME/CNE Credit:** To encourage the completion of online trainings and the attendance at site meetings, providers and nurses will be offered CME/CNE credit for completing learning modules, and MOC/QI credit for attending office systems change meetings and reviewing practice rates.

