Additionally, subjects completing the above surveys will be entered into a drawing for a \$75 gift card for each survey completed. Health systems will have the ability to opt out of this additional drawing incentive if it conflicts with their institutional policy. Disclosure of the approximate chances of winning, and when required per institutional policy, procedures for the inclusion of those who do not wish to complete the survey will be included in the survey invite e-mail and Information Sheets. Winners will be chosen at random using a secure computer-generated randomization program containing the names of all participating subjects. Winners will be notified within 48 hours of being selected. Payment will be sent to the winners using the contact information collected in the address/e-mail field of their REDCap survey.

For serving as an intervention site, a single practice-level payment will be offered in the amount of \$250. This payment will be in the form of a gift card or check, and will be disseminated to the vaccine champion from each intervention location. Payment may be used for any practice-wide item(s) deemed beneficial by the vaccine champion. If manual chart review is necessary at a practice site (and thus additional payment to the vaccine champion is made), the \$250 practice-level payment for that site will be reduced by the total payout amount for the manual chart review.

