### Final Time/Cost Analysis:

Upon completion of aim/phase 2 we will conduct a final time/cost analysis. Our two-fold cost measures are (a) total intervention cost to implement the VAX-MOM program aggregated at the four health-system level under a cost analysis and (b) cost per additional flu or Tdap vaccination under a subsequent cost-effectiveness analysis. To derive a policy implication regarding the sustainability of programs, we will estimate costs and ICER estimates from the health system perspective.

**Total Cost:** To make these cost measures comparable to similar past interventions of reminders and educational programs, we will estimate cost with one-year time horizon, excluding the cost to purchase, store and administer vaccines. We will estimate the total intervention cost, summing non-personnel costs (e.g., EHR hardware, software, and materials) and personnel costs. The personnel costs will distinguish research costs from intervention costs (e.g., practice-level meeting and collecting EHR data). The dollar values of these personal costs will be calculated by multiplying “time efforts” (weekly reported by study personnel using a REDCap email survey) with the nationally representative “hourly-wage rates” by occupation codes of study personnel, derived from the Bureau of Labor Statistics.

**Cost-Effectiveness:** We will develop a standard decision model for our cost-effectiveness analyses. The effectiveness measures are the rates of flu and Tdap vaccination estimated under Aim 2b.

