As explained above, this intervention cost will exclude the cost to purchase, store and administer vaccines, which is assumed to be identical among all practices. Applying the same assumption, the average cost for the control group (costControl) is zero. To make separate ICER estimates for flu and Tdap vaccination, the Tdap-vaccination-specific costStudy will be estimated during non-flu season (April to September) first and applied for calculating the flu-vaccination-specific costStudy during a flu season (October to March), assuming the Tdap-vaccination-specific costStudy is constant throughout a year. Using the developed standard decision model, we will conduct probabilistic analyses to generate point estimates and 95% CIs for ICERs and one-way sensitivity analyses to determine conditions for being lower than the thresholds of cost-effectiveness, e.g., healthcare-system based quality improvement interventions to improve flu vaccination uptake targeting general populations (median ICER \$51 among 23 interventions) and healthcare workers (median ICER \$125 among 6 interventions) reported by a systematic review.

Hyp. : Cost per additional flu or Tdap vaccination under the VAX-MOM is lower than past similar interventions.

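### Personnel time is priced at bare hourly wages although the costing takes the health-system perspective, so labour cost and the ICER are understated

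*Combined protocol and SAP*

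**What the plan says.** Section 17, Final Time/Cost Analysis, sets the viewpoint: "we will estimate costs and ICER estimates from the health system perspective". The total is built by "summing non-personnel costs (e.g., EHR hardware, software, and materials) and personnel costs". Personnel cost is hours times price. The hours are "weekly reported by study personnel using a REDCap email survey", and the price is "nationally representative “hourly-wage rates” by occupation codes of study personnel", taken from the Bureau of Labor Statistics. No part of the documents adds fringe benefits, employer taxes or overhead to that wage.

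The cost-effectiveness text then states that "the average cost for the control group (costControl) is zero". It plans probabilistic analyses and one-way sensitivity analyses against benchmark medians of $51 and $125 per additional vaccination, and it hypothesises that VAX-MOM will be cheaper than similar past programmes. It does not list which inputs the one-way analyses will vary.

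Section 12 describes payments on the intervention side. One reads "For serving as an intervention site, a single practice-level payment will be offered in the amount of" $250; another is $5 to the vaccine champion for each PDSA survey and each Time & Cost survey, up to $120. In section 4, Step 1, the item on MOC/CME/CNE credit says: "To encourage the completion of online trainings and the attendance at site meetings, providers and nurses will be offered CME/CNE credit".

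**The concern.** The perspective determines the price. A health system deciding whether to sustain the programme bears the full employment cost of each hour, not only the wage. A wage-only price is therefore a systematic shortfall on every hour counted, and it always has the same sign. Because the comparator's cost is fixed at zero, the shortfall passes straight into the incremental cost. It lowers VAX-MOM's own cost per additional vaccination, which is the direction of the stated hypothesis.

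The point is the price attached to each hour. Whose hours are counted is a separate question and is not raised here.

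**Working it through.** **Inputs from the documents.** Price per hour: the wage only (section 17, Total Cost). Control cost: 0 (section 17, cost-effectiveness text). Benchmarks: $51 and $125 (same place). Effect: 6.3 percentage points, with 5,000 women in 16 practices per arm, ICC 1%, test-level alpha 0.025 (section 17, Power Analysis). Site payment: $250 (section 12).

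**Assumptions, not in the documents.** Fringe rate f: 20-45% of wages. Personnel share s of the bare-wage intervention cost: 50-100%.

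**Step 1, labour cost.** True labour cost = wage cost × (1 + f), so the understatement is 1 − 1/(1 + f).
- f = 0.20: 1 − 1/1.20 = 16.7%
- f = 0.45: 1 − 1/1.45 = 31.0%

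**Step 2, ICER.** With control cost zero, ICER = C/E, where C is intervention cost and E is additional vaccinations (taken as positive). Loading the wage changes C to C × (1 + s × f), so the ICER is multiplied by 1 + s × f.
- s = 0.5, f = 0.20: factor 1.10, an understatement of 1 − 1/1.10 = 9.1%
- s = 1.0, f = 0.45: factor 1.45, an understatement of 31.0%

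A bare-wage ICER of 51/1.10 = $46.36 in the first case, or 51/1.45 = $35.17 in the second, would already equal $51 once loaded. E cancels, so this step does not depend on the size of the effect.

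**Step 3, the plan's own figure.** The documents state no total cost or ICER to reproduce. The power statement supplies a number of additional vaccinations, and it can be checked. With 5,000 per arm, the mean practice size is 5,000/16 = 312.5, the design effect is 1 + 311.5 × 0.01 = 4.115, and the effective n is 5,000/4.115 = 1,215 per arm. Power is then 80.8% from a 49% base and 81.6% from a 54% base, which reproduces the stated value above 80%. Reading 5,000 as the total for both arms gives 70.9% and 71.8%, so it must be per arm. Additional vaccinations at that effect: 5,000 × 0.063 = 315 per vaccine.

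**Step 4, scenario for the site payment only.** 16 × $250 = $4,000. Charged to one vaccine this is 4,000/315 = $12.70 per additional vaccination; spread over both it is 4,000/630 = $6.35. Against $51 that is 25% and 12%.

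**The case against.** The best defence of bare wages is comparability. The plan wants a figure that can be set beside past programmes, and if those also used bare wages, loading only VAX-MOM would make the comparison less fair. Part of this stands: the documents do not show how the $51 and $125 benchmarks priced labour, so a net bias in the comparison with them is not established. It does not justify the base case. The plan's stated comparability choices are the one-year horizon and the exclusion of vaccine purchase, storage and administration; wage pricing is not among them. The unspecified sensitivity analyses do not clearly cover the gap either.

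A reader might also infer that the payments and credits given only to intervention practices are left out, and that this further understates the ICER. The documents do not support that, for four reasons.
- The non-personnel class is illustrated with examples, not closed, so a site payment could fall within it. The statement "The personnel costs will distinguish research costs from intervention costs" concerns personnel costs only and leaves the payments unclassified.
- Nothing says that the health system pays them. Section 12 lists them beside compensation for research surveys.
- The $5 PDSA payment is for completing a survey sent to study staff, so it can be read as research compensation.
- The $250 may be spent on any practice-wide item. Only the credits are described as encouragement, and no cost is given for them.

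Adding these payments could also count some resources twice if the monthly Practice Time & Cost Survey (section 4, Step 4) captures the same time or money.

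**Conclusion.** The wage point holds. Followed as written, the costing rule understates labour cost from the stated perspective, and therefore the ICER, whenever employer cost exceeds the wage and the programme yields additional vaccinations. The direction follows from the plan's own formula; the size does not. The 17-31% applies to labour cost and rests wholly on an assumed fringe rate of 20-45%. The ICER effect, 9-31% on the further assumption of a 50-100% personnel share, cannot be fixed from the documents.

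Whether the shortfall would reverse a conclusion against $51 or $125 is unknown, because neither VAX-MOM's cost nor the benchmarks' labour pricing is given. The payments do not support a claim of understatement. The $6.35-$12.70 shows only how much their classification could matter, and its denominator of 315 is the detectable difference in the power statement, not a forecast. This is a minor point about a secondary economic analysis.

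**What to change.** In the Total Cost paragraph of section 17:
- Multiply each hourly wage by (1 + a stated fringe rate) in the base case, and give the source of the rate.
- Name that rate as an input to the one-way sensitivity analyses, with a range.
- Report the bare-wage ICER as a sensitivity analysis, for comparability with benchmarks whose labour pricing is not shown.

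At most, add a scenario ICER that includes the $250 site payment, without moving it into the base case.

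The cost is one multiplier in the costing sheet and an extra reported line or two, with no new data collection. The downside is a less favourable cost figure.

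### Equal vaccine cost per dose does not cancel in a cost per additional vaccination, so the planned ICER is a programme-cost ratio and does not by itself support a health-system sustainability conclusion

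*Combined protocol and SAP*

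**What the plan says.** Section 17, Final Time/Cost Analysis, defines the second cost measure as "cost per additional flu or Tdap vaccination under a subsequent cost-effectiveness analysis". On perspective it says "we will estimate costs and ICER estimates from the health system perspective", and it links this to the sustainability of such programmes.

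Two reasons are given for leaving vaccine costs out.

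- **Comparability.** Under Total Cost, the plan begins "To make these cost measures comparable to similar past interventions of reminders and educational programs" and continues "we will estimate cost with one-year time horizon, excluding the cost to purchase, store and administer vaccines".
- **Equality across practices.** Under Cost-Effectiveness, the excluded item is "the cost to purchase, store and administer vaccines, which is assumed to be identical among all practices". The next sentence builds on this: "Applying the same assumption, the average cost for the control group (costControl) is zero".

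The resulting ICERs, one for flu and one for Tdap, are compared with two published thresholds: "median ICER \$51 among 23 interventions" for general populations and "median ICER \$125 among 6 interventions" for healthcare workers. The only stated hypothesis is that the cost per additional vaccination is lower than in similar past interventions. Probabilistic and one-way sensitivity analyses are planned, but vaccine cost is not named among the inputs to be varied.

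**The concern.** A cost can be dropped from an incremental ratio when its total is the same in both arms. The plan's second reason speaks of sameness among practices, which is at most sameness per dose. The denominator of the ratio is extra vaccinations, so whenever the ratio is defined the arms differ in the number of doses given. The vaccine cost of those extra doses belongs in the numerator if the ratio is to speak for the health system.

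What is at stake is the sustainability conclusion. A health system deciding whether to keep the programme needs the net cost of each extra dose as well as the cost of training, prompts and feedback. The protocol's own account of barriers (Section 2) lists financial obstacles for providers, and difficulty with buying and storing vaccine for systems. A ratio that sets these items to zero should not be reported as the health system's cost of an extra vaccination.

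**Working it through.** **Inputs from the plan** (Section 17, Data Analysis Plan): control rates p = 0.49 (flu) and 0.54 (Tdap); effect δ = 0.063; ICC 0.01; two-sided alpha 0.025; 5,000 women and 16 practices per arm; thresholds $51 and $125. The plan states no ICER, programme cost or cost per dose, so the power statement is the only related figure that can be reproduced.

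**Step 1: reproduce the power statement.** Taking the 5,000 as per arm:

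- women per practice = 5,000/16 = 312.5
- design effect = 1 + (312.5 − 1) × 0.01 = 4.115
- effective n per arm = 5,000/4.115 = 1,215
- power = 80.8% for flu (49% against 55.3%) and 81.5% for Tdap (54% against 60.3%)

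The claim of more than 80% power reproduces on that reading. If 5,000 were the total, power would be 70.9% and 71.8%, so I use 5,000 per arm below.

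**Step 2: does the vaccine cost cancel?** Let c be the net cost per dose (buying, storing and giving it, less payment received), equal in every practice. Let N be the women per arm and I the programme cost.

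- Control arm vaccine cost: `c × N × p`
- Intervention arm vaccine cost: `c × N × (p + δ)`
- Difference: `c × N × δ`, which is zero only if c = 0 or δ = 0

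Planned ICER = `I / (N × δ)`.

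Vaccine-inclusive ICER = `(I + c × N × δ) / (N × δ)` = planned ICER + c.

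The gap is c whatever the effect size or number of women. At the design effect, intervention practices give 0.063/0.49 = 12.9% more flu doses and 0.063/0.54 = 11.7% more Tdap doses per woman than control practices.

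**Step 3: allow for better recording.** The training content (Table 3) includes documenting vaccines given offsite, and the outcome is vaccination as recorded in the EHR. If a fraction q of the added recorded vaccinations are doses that the system neither bought nor gave, the gap becomes `(1 − q) × c`. So c is the most by which the average can shift.

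**Step 4: size for assumed values of c.** At the design effect there are 5,000 × 0.063 = 315 additional doses per vaccine. A programme cost of 315 × $51 = $16,065 would just meet the first threshold, and 315 × $125 = $39,375 the second. The values of c below are assumptions for illustration, with q = 0:

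| Assumed c | Omitted amount (315 × c) | Planned $51 becomes | Planned $125 becomes |
|---|---|---|---|
| −$20 | −$6,300 | $31 | $105 |
| $0 | $0 | $51 | $125 |
| $20 | $6,300 | $71 | $145 |
| $50 | $15,750 | $101 | $175 |
| $100 | $31,500 | $151 | $225 |

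The dose count affects only the second column. Using the Table 6 deliveries instead, 14,416/2 × 0.063 = 454 doses per vaccine, assuming an even split between arms and that every delivery counts. The shift in the ratio is still c.

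**The case against.** The strongest defence is that the exclusion is deliberate, disclosed and separately justified by comparability, and that the only stated hypothesis is the comparison with past programmes. That stands. If the $51 and $125 medians also leave vaccine costs out, the comparison is like for like and should stay as planned. Whether they do cannot be told from the documents.

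Four stronger readings are tempting, and the documents do not support them.

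- **That the identical-cost assumption must be false.** Read as a cost per dose, it can be true. The fault is that it does not justify the exclusion.
- **That the health-system ICER is too favourable.** The documents give no vaccine price, administration cost or payment. Table 6 shows private and public insurance, so payment is plausible. If payment covers the dose the gap is nil, and if it exceeds the cost the sign reverses.
- **That the ratio is wrong by exactly one dose cost.** Better recording of offsite doses would make the average shift smaller.
- **That c can be expressed as a percentage of the $51 benchmark to show how serious the gap is.** That would set a vaccine cost against a figure whose cost basis is unknown.

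Nor can it be said that the planned sensitivity analyses exclude vaccine cost. The plan does not list their inputs; it only fails to name this one.

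Setting the control cost to zero is also defensible for programme cost alone, because control practices stay on standard of care (Section 4). That ground does not depend on equal vaccine costs.

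**Conclusion.** The point holds in a limited form. The planned ratio measures programme cost per additional vaccination. Equal unit cost does not turn it into a health-system ICER, because the net cost of each added dose remains in the increment. The vaccine-inclusive figure differs from the planned one by c, or by a smaller amount if part of the measured gain is documentation.

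This rests on c being the same in every practice, as the plan assumes, and on the health system bearing the net cost of the doses it gives. The value and sign of c are not in the documents, so neither the size nor the direction of the error is known.

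The effect is confined to the sustainability conclusion of a secondary economic analysis. The benchmark hypothesis is affected only if the benchmarks include vaccine costs. The co-primary flu and Tdap comparisons are unaffected.

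**What to change.** In Section 17, Cost-Effectiveness:

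1. Delete the statement that vaccine costs are identical among practices as a reason for the exclusion. Keep comparability as the reason, and state whether the $51 and $125 benchmarks exclude vaccine costs.
2. Label the planned ratio as programme cost per additional vaccination and use it for the benchmark comparison. Justify the zero control cost by the absence of a programme in control practices.
3. For the health-system conclusion, also report that ratio plus the net cost per dose, separately for flu and Tdap.
4. Name net cost per dose as an input to the planned one-way and probabilistic analyses, over a range that includes zero. If the data allow, vary the share of added vaccinations that are offsite doses.

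The cost is some rewording and one sourced input per vaccine. The reported health-system ICER may become less favourable.

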- **E-learning platform:** Module content will first be disseminated to practice site personnel via an online e-learning platform (i.e., Articulate). Study coordinators will obtain e-mail addresses for the site personnel from either the health system liaison or the associated vaccine champion, and will then e-mail a training content link to all appropriate site providers, nurses, and staff. Attached to this initial e-mail will be an Information Sheet describing the study goals and training phase details, as well as their involvement throughout the duration of the 12-month QI intervention (see “*TrainingPhaseEmail...*” and “*InformationSheetTrainingPhase...*” documents; also see “Consent Process” section for more detail). After reviewing the Information Sheet and discussing any questions/concerns with study staff, site personnel will be asked to access and complete the training lessons prior to their scheduled site meeting.

Embedded at the conclusion of the online training module, will be a link to a brief REDCap survey (see “*TrainingModuleCompletionSurvey...*” document) to obtain information regarding those who have fully completed the training. A list of practice personnel who have successfully completed the online training will be stored in a password-protected Excel/Word file by each study coordinator. The names will not be linked with any other study data. The list will be accessible only by study staff for the purposes of confirming those who should receive CME/CNE credit.

Note: For intervention sites that have completed the e-learning training during the first half of the calendar year (i.e., prior to July), site personnel may be asked to additionally complete an abbreviated “flu booster” e-learning module just prior to flu season of that same year (e.g., in Aug/Sept). This abbreviated version (approx. 15 minutes to complete) will contain content (see table 3) only applicable to influenza.

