## **Step 2) Monitor adoption of VAX-MOM training content at randomized practices:**

To monitor the adoption of VAX-MOM training content (changes in communication techniques, workflow optimization, etc.) at each practice site, each vaccine champion will participate in the following activities in an ongoing basis:

1. *Lead a discussion regarding immunization rate feedback* with practice providers, nurses, and staff on a bi-monthly basis (every-other month). The champion will monitor the site personnel attending each feedback discussion as well as their role (e.g., Ob/Gyn, nurse, desk staff, etc.) within the practice. They will e-mail study staff with a list of individual attendees for the purposes of tracking those receiving MOC credit. They will also report aggregate numbers on a monthly basis using the “Practice Time & Cost Survey.”

The site-specific flu and Tdap vaccination rates will be obtained from either: 1) the EHR report builders for each health system (*possible for all 4 health systems*), or 2) manual chart review (*possible for only NY health systems*). Obtained rates will be sent either via secure e-mail directly to the study coordinator in each corresponding state, or uploaded to the secure shared Box folder. The study coordinator will then disseminate the vaccination rates for each site to all corresponding site personnel (see “*RateFeedbackTemplate...*” document).

2. *Develop PDSA cycles/goals* on a monthly basis utilizing knowledge about current workflow efficiency and data from vaccine rate reports. Vaccine champions will utilize the PDSA template (see “*PDSASurvey...*” document) to guide progress with their respective teams. The template will help them decide upon specific

intervention activities appropriate for their setting, track those involved with each activity, compare results from the activity to previous performance, and focus on changes that may need implementation during future cycles. PDSA cycle logs will be shared with study staff via a secure REDCap survey (same “*PDSASurvey...*” document formatted on the REDCap platform) sent to the vaccine champion each month by the appropriate study coordinator.

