**Table 5. EHR Data Extraction Categories**

Primary	

• Flu vaccines received during flu season (Sept-April)

• Tdap vaccines received during 27-36 weeks of pregnancy

Secondary	

• Vaccine refusal (as documented in EHR)

• Missed opportunities for flu and Tdap

• Flu vaccine in prior season

• Covid vaccination

Patient Demographics	

• Race/ethnicity

• Age

• Insurance

• Language

• Parity

Practice Demographics	

• Site

• Provider type (resident, midwife, MD)

- Measure Procedures

Each health system [REDACTED] will have its own “report builder.” The report builder will be in charge of collecting the electronic health record (EHR) data from their own health system and putting it into a format (report) that can be easily understood and analyzed by study staff.

*Bi-Monthly Feedback Reports:* The report builder for each health system will create vaccine rate feedback reports utilizing extracted EHR data for intervention sites on a bi-monthly basis. These reports will be sent either via secure e-mail directly to the study coordinator in each corresponding state, or uploaded to the secure shared Box folder. The study coordinator will then disseminate the vaccination rates for each site to all corresponding site personnel.

For NY health systems, in the event an automated EHR feedback report cannot be generated in time for any given month, the identified vaccine champions or study personnel will estimate flu and Tdap vaccine rates via manual chart review. All vaccine champions and/or study personnel conducting manual chart review will have completed all appropriate eRecord training prior to accessing patient charts. Of those patients who delivered during the identified month, at least 20% will be reviewed. For each chart reviewed, the vaccine champion or study personnel will document the receipt (or lack thereof) of influenza and Tdap immunization as well as Covid vaccination when possible, and will share results with the study team via secure e-mail.

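### The cost split treats April–September as non-flu while Table 5 counts flu vaccines September–April, so the separate flu and Tdap cost-effectiveness ratios may be distorted

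*Combined protocol and SAP*

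**What the plan says.** Section 17 plans separate incremental cost-effectiveness ratios (ICERs) for the two vaccines. The Tdap-specific cost "will be estimated during non-flu season (April to September) first". It is then "applied for calculating the flu-vaccination-specific costStudy during a flu season (October to March"), "assuming the Tdap-vaccination-specific costStudy is constant throughout a year". Control-arm cost is set to zero, so each numerator is simply the intervention cost assigned to that vaccine. The horizon is one year. The ratios are to be judged against published benchmarks (medians of $51 and $125) and against a hypothesis that the programme costs less per extra vaccination than comparable earlier ones.

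Table 5 (Section 4, Step 3) gives the flu outcome as "Flu vaccines received during flu season (Sept-April"). The Tdap outcome is tied to gestational weeks, not to the calendar.

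Section 4, Step 1 adds that sites which have "completed the e-learning training during the first half of the calendar year (i.e., prior to July") may be asked to take an abbreviated, influenza-only "e-learning module just prior to flu season of that same year (e.g., in Aug/Sept"), and the parallel provision covers a second "site meeting just prior to flu season of that same year (e.g., in Aug/Sept"). Each lasts about 15 minutes.

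Other activities serve both vaccines. The start-up training in Table 3 covers both. Step 2 feeds back the two rates together ("The site-specific flu and Tdap vaccination rates will be obtained from either" automated reports or chart review) and asks for monthly PDSA cycles.

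**The concern.** The seasonal device works only if April–September holds no flu-specific cost. The plan's own flu season includes two of those six months, and its flu-only boosters are placed in the same window. Section 17 states no step that removes flu effort before the April–September figure is called Tdap-specific. Because that figure is also carried into October–March, any flu cost inside it would count twice against Tdap and be taken off flu. Start-up training that serves both vaccines would be assigned by when it happened to be scheduled.

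At stake are the two separate ICERs and the hypothesis tested with them. With control cost at zero, an allocation error passes in full proportion into the ratio.

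**Working it through.** **1. The months side by side** (both ranges read as inclusive)

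| Months | Cost split, Section 17 | Flu outcome, Table 5 |
|---|---|---|
| October–March | flu | flu |
| April, September | non-flu | flu |
| May–August | non-flu | not flu |

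The definitions disagree on 2 of Section 17's 6 non-flu months, which are 2 of Table 5's 8 flu months. August may also hold boosters. I assume that the ICER's effect uses Table 5's flu outcome; Section 17 refers to rates from an Aim 2b that the supplied text does not define.

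**2. The split as algebra.** Section 17 does not define 'applied'; I read it as subtraction. Let:
- a = monthly Tdap cost plus recurring shared cost, assumed even over the year
- f, g = flu-only cost in April–September and in October–March
- J = one-off joint training inside the horizon, with share p dated October–March

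Then:
- April–September cost N = 6a + f + (1−p)J
- October–March cost F = 6a + g + pJ
- Tdap cost = 2N = 12a + 2f + 2(1−p)J
- Flu cost = F − N = g − f + (2p−1)J
- Sum = N + F = 12a + f + g + J, which is the correct total

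Flu-only cost is really f + g, so flu is understated by 2f and Tdap overstated by 2f. Each dollar of joint training goes wholly to flu if dated October–March. If dated April–September it adds $2 to Tdap and takes $1 off flu.

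**3. Illustrations.** The plan gives no cost figures to reproduce, so all units here are assumed. Take a = 100 per month, g = 600, J = 0.
- f = 60: N = 660, F = 1,200. Tdap = 1,320 against 1,200 (+10%); flu = 540 against 660 (−18%).
- f = 120: N = 720, F = 1,200. Tdap = 1,440 against 1,200 (+20%); flu = 480 against 720 (−33%).

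With f = 0 and J = 600, flu cost is 600 − 600 = 0 if the training is dated April–September, and 600 + 600 = 1,200 if dated October–March.

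In shares, with C = f + g and s = f/C, planned flu cost is (1−2s)C + (2p−1)J. With J = 0 this is 0.90C at s = 0.05 and 0.80C at s = 0.10. With J = 0.2C it is 1.10C and 1.00C if all training is dated October–March, and 0.70C and 0.60C if all is dated April–September.

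**4. Documented size.** The only flu-only effort that the plan explicitly places in the window is at most 15 + 15 = 30 minutes per person, and only at sites trained before July. Flu work in April and September is not quantified.

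**5. A May–August rate.** Suppose a share u of C falls untagged in May–August. The monthly rate rises by uC/4. Subtracting twelve months of it from the annual recurring cost leaves C − 12(uC/4) = (1−3u)C. This beats (1−2s)C only if u < 2s/3. With s = 0.10 and u = 0.02 it gives 0.94C against 0.80C. With s = 0.05 and u = 0.05 it gives 0.85C against 0.90C, which is worse.

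**The case against.** The strongest reply is that Section 17 speaks of a Tdap-specific cost. If the Time & Cost survey forms, which were not supplied, record time by vaccine, flu-only time never enters the April–September figure and nothing leaks. 'Applied' is also undefined, and cost symbols appear without a formula in the supplied text, so something may have been lost in extraction. The documented booster time is small. These points stand: the leak is conditional. They do not remove the month conflict, which is exact.

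A reader might infer that the plan has no rule for shared costs. That goes too far. Subtraction implies one: recurring shared cost that is even over the year cancels from flu and falls wholly on Tdap. Costing flu as an increment in this way is a legitimate convention, so the documents do not show it to be an error. If shared work instead intensifies in flu season, the excess falls on flu.

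A reader might also infer that the flu ICER is biased downward. The documents do not settle this. The timing of joint training can offset, reverse or deepen the window effect; one case above lands on exactly 1.00C. The timeline figure is not shown, and training in the first half of the year spans both cost windows.

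**Conclusion.** The point holds as an inconsistency between Section 17 and Table 5 that can distort the separate flu and Tdap ICERs. Given subtraction and surveys that do not tag time by vaccine, the error is 2f in each direction for flu-only cost f in April–September, and joint training is assigned by date. Neither the size nor the net direction for flu can be stated, because the plan gives no costs or training dates; the illustrations show the mechanism only. Total intervention cost and the primary vaccination comparison are untouched. This is low priority: a secondary economic analysis, with no ICER listed in Table 4.

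**What to change.** Amend Section 17 as follows:
- State what 'applied' means, and use Table 5's flu season in the cost split.
- Book flu-only booster time directly to flu.
- Take one-off joint start-up training out of the monthly costs. State how it is divided between the vaccines, and vary that division in the one-way sensitivity analyses already planned.
- Estimate the recurring Tdap rate from May–August after those removals. Recurring flu cost is the 12-month recurring cost minus 12 times that rate; add booster time and flu's stated share of training. Tdap cost is the total minus flu cost.
- If the survey forms tag time by vaccine, use the tags instead.

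The cost is a wording change and use of data already planned. Practice surveys are monthly. Study-staff surveys are weekly in Step 4 and Section 17 but monthly in Step 2; either dates cost by month. Booster and start-up time must be identifiable from the surveys or training records. If August boosters cannot be isolated, May–July remains.

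The downsides are four rather than six months to estimate the rate, and reliance on recurring shared cost being even over the year. The gain also needs little untagged flu cost in May–August (u below 2s/3).
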